### **1.3 Exploratory Objectives**

- Correlative laboratory studies of subjects including gene expression profiling and molecular analysis to determine the in vivo mechanism of action and the molecular and biological effects of the combination of decitabine and eltrombopag will be performed.

## **2. BACKGROUND AND SCIENTIFIC RATIONALE**

### **2.1 Background**

Myelodysplastic syndromes (MDS) are malignant clonal disorders characterized by ineffective hematopoiesis, bone marrow dysplasia, peripheral cytopenias including thrombocytopenia, and a propensity to transform into acute myeloid leukemia (AML). Classically, MDS is associated with apoptosis and excessive proliferation, resulting in a paradoxical combination of a hyper-cellular marrow and peripheral cytopenias. The incidence of MDS in the United States is rising, with approximately 20,000 to 30,000 new cases of MDS diagnosed annually, and a median age at diagnosis of 70 years.

Over the past decade, clinical use of the hypomethylating agent decitabine has been shown to improve patient quality of life, decrease transfusion requirements, and improve outcome parameters in MDS patients, and is now a standard of care for MDS patients requiring therapy. However, myelosuppression including severe thrombocytopenia is commonly seen in decitabine-treated patients, and is the most frequent cause of dose reduction, delay and discontinuation of the HMA agents (including both decitabine and 5-azacitidine) in up to 80% of patients. With current HMA regimens, achievement of an ORR is estimated at 28-70%, with a CR rate of only 6-34% in patients treated with front-line HMA therapy, and with a median length of response in the HMA-responders of only 8 to 10 months.

As alluded to above, the platelet count in MDS patients is critically important, and impacts both treatment decisions and overall survival in the majority of MDS patients. Among 2410 patients with MDS referred to the MD Anderson Cancer Center, 67% had a platelet count  $<100 \times 10^9/L$  at the time of their initial consultation, with over 10% of patients presenting with life-threatening thrombocytopenia ( $<20 \times 10^9/L$ ). The frequency of hemorrhagic deaths within this population ranged from 14 to 24%.

Thrombocytopenia has been identified as an independent and adverse prognostic factor for overall survival in MDS at all stages. An analysis of 892 primary MDS subjects identified a median survival in patients with platelet counts  $< 100 \times 10^9/L$  of 27 months, compared to 60 months for patients with platelet counts  $\geq 100 \times 10^9/L$ . Furthermore, the mainstay of treatment for thrombocytopenia in MDS patients, transfusions, are short-lived, and associated with transfusion reactions, allo-immunization, transmission of bacterial and viral infections, and have no impact on the underlying disease biology.

Given the high rate of thrombocytopenia both prior to and during decitabine therapy, which can result in inadequate treatment due to dose reductions and therapy delay, as well as the risks of hemorrhagic complications, the addition of eltrombopag to improve thrombocytopenia in MDS patients is justified. Furthermore, the anti-leukemia properties of eltrombopag seen both *in vitro* and in early clinical studies, identify eltrombopag as an excellent candidate agent for this purpose.

## 2.2 Rationale for Use of Eltrombopag and Dose Selection

Eltrombopag (Promacta), a second-generation thrombopoietin-receptor agonist (TPO-RA), is a synthetic small-molecule oral thrombopoietin mimetic that binds to c-MPL,

promoting megakaryopoiesis and release of platelets from mature megakaryocytes. It is currently FDA-approved for the treatment of immune thrombocytopenic purpura (ITP) and hepatitis C (HCV) associated thrombocytopenia. Eltrombopag has a unique mechanism of action compared to the other TPO-RAs, and functions through binding to a transmembrane domain of the TPO-receptor, activating the JAK/STAT pathway but producing much less activation of the STAT family, and without activation of the Akt pathway. Intriguingly, in cell lines and in Phase I clinical studies, eltrombopag has shown anti-leukemia activity unrelated to the TPO-RA pathway, leading to a modest inhibition of leukemia or MDS cell growth, while continuing to simulate normal megakaryopoiesis in bone marrow samples, and has also been associated with multilineage clinical responses in patients with severe and refractory aplastic anemia.

This study will enroll patients with advanced MDS, defined as IPSS Int-2 or high-risk MDS, or IPSS-R high or very-high MDS and with thrombocytopenia with a platelet count < 100K. The study will explore the supportive care and disease-modifying effects of eltrombopag in addition to decitabine standard of care treatment for advanced MDS. In patients with advanced MDS receiving decitabine, the consequences of low platelet counts, namely platelet transfusions and hemorrhage, form the basis of clinical outcomes which provide clinically meaningful benefit.

Optimal dosing of eltrombopag is adjusted, based upon platelet count response in individual patients. The starting dose of eltrombopag selected for this study is 100mg (50mg for East Asian patients). Dose modifications will be permitted, from a minimum dose of 25mg to a maximum dose of 300mg in order to maintain platelet counts at a safe and effective level. This is based upon the observed efficacy, safety and pharmacokinetics of studies including PMA112509 (NCT009034) and TRC114968 (NCT014403). In both studies, the majority of subjects were escalated to the maximum dose of 300mg (150mg for East Asian patients). The safety profile of eltrombopag at these doses was similar to prior studies at lower doses (i.e. 50mg in ITP registry studies). No new safety signals were identified, and the frequency and intensity of AEs known to be associated with eltrombopag (e.g. elevation in liver enzymes) were not increased despite the higher doses. Additional trials of lower-risk and higher-risk MDS patients with thrombocytopenia have shown daily eltrombopag, dosed from 50mg to up to 300mg daily, is safe and effective in the MDS population.

## **2.3. Eltrombopag Safety Profile:**

### **2.3.1 Hepatotoxicity**

Eltrombopag may cause hepatotoxicity. In the controlled clinical trials in chronic ITP, one patient experienced Grade 4 (NCI Common Terminology Criteria for Adverse Events [NCI CTCAE] toxicity scale) elevations in serum liver test values during therapy with eltrombopag, worsening of underlying cardiopulmonary disease, and death. One patient in the placebo group experienced a Grade 4 liver test abnormality. Overall, serum liver test abnormalities (predominantly Grade 2 or less in severity) were reported

in 11% and 7% of the eltrombopag and placebo groups, respectively. In the 3 controlled chronic ITP trials, four patients (1%) treated with eltrombopag and three patients in the placebo group (2%) discontinued treatment due to hepatobiliary laboratory abnormalities. Seven of the patients treated with eltrombopag in the controlled trials with hepatobiliary laboratory abnormalities were re-exposed to eltrombopag in the extension trial. Six of these patients again experienced liver test abnormalities (predominantly Grade 1) resulting in discontinuation of eltrombopag in one patient. In the extension study chronic ITP trial, one additional patient had eltrombopag discontinued due to liver test abnormalities ( $\leq$ Grade 3).

In 2 controlled clinical trials in patients with chronic hepatitis C and thrombocytopenia, ALT or AST  $\geq 3X$  ULN was reported in 34% and 38% of the eltrombopag and placebo groups, respectively. Most patients receiving eltrombopag in combination with peginterferon/ribavirin therapy will experience indirect hyperbilirubinemia. Overall, total bilirubin  $\geq 1.5 X$  ULN was reported in 76% and 50% of patients receiving eltrombopag and placebo, respectively.

Measure serum ALT, AST, and bilirubin prior to initiation of eltrombopag, every 2 weeks during the dose adjustment phase, and monthly following establishment of a stable dose. If bilirubin is elevated, perform fractionation. Evaluate abnormal serum liver tests with repeat testing within 3 to 5 days. If the abnormalities are confirmed, monitor serum liver tests weekly until the abnormality(ies) resolve, stabilize, or return to baseline levels. Discontinue eltrombopag if ALT levels increase to  $\geq 3X$  (ULN) in patients with normal liver function or  $\geq 3X$  baseline in patients with pre-treatment elevations in transaminases and are:

- progressive, or
- persistent for  $\geq 4$  weeks, or
- accompanied by increased direct bilirubin, or
- accompanied by clinical symptoms of liver injury or evidence for hepatic decompensation.

Reinitiating treatment with eltrombopag is not recommended. If the potential benefit for reinitiating treatment with eltrombopag is considered to outweigh the risk for hepatotoxicity, then cautiously reintroduce eltrombopag and measure serum liver tests weekly during the dose adjustment phase. If liver tests abnormalities persist, worsen or recur, then permanently discontinue eltrombopag.

### **2.3.2. Bone Marrow Reticulin Formation and Risk for Bone Marrow Fibrosis**

Eltrombopag may increase the risk for development or progression of reticulin fiber deposition within the bone marrow. In the extension trial in chronic ITP, 151 patients have had bone marrow biopsies evaluated for increased reticulin and collagen fiber deposition. Bone marrow biopsies taken after 1 year of therapy showed predominantly myelofibrosis (MF) Grade 1 or less in 140/151 (93%) of patients. There were 11/151 (7%) of patients with MF Grade 2. Four patients had collagen deposition reported. One patient with a pre-existing MF Grade 1 developed a MF Grade 2 and subsequently discontinued treatment with eltrombopag. Clinical trials have not excluded a risk of bone marrow fibrosis with demonstrated clinical consequences to date. If new or worsening blood morphological abnormalities or cytopenias occur, consider a bone marrow biopsy including staining for fibrosis.

### **2.3.3. Thrombotic/Thromboembolic Complications**

In 2 controlled clinical trials in patients with chronic hepatitis C and thrombocytopenia, (31/955) treated with eltrombopag experienced a thrombotic event compared to 1% (5/484) on placebo. The majority of events were of the portal venous system (1% in patients treated with eltrombopag versus <1% for placebo).

Thrombotic/thromboembolic complications may result from increases in platelet counts with eltrombopag. Reported thrombotic/thromboembolic complications included both venous and arterial events and were observed at low and at normal platelet counts.

Consider the potential for an increased risk of thromboembolism when administering eltrombopag to patients with known risk factors for thromboembolism (e.g., Factor V Leiden, ATIII deficiency, antiphospholipid syndrome, chronic liver disease). To minimize the risk for thrombotic/thromboembolic complications, do not use eltrombopag in an attempt to normalize platelet counts. Follow the dose adjustment guidelines to achieve and maintain a target platelet count.

In a controlled trial in non-ITP thrombocytopenic patients with chronic liver disease undergoing elective invasive procedures (N = 292), the risk of thrombotic events was increased in patients treated with 75 mg eltrombopag once daily. Seven thrombotic complications (six patients) were reported in the group that received eltrombopag and three thrombotic complications were reported in the placebo group (two patients). All of the thrombotic complications reported in the group that received eltrombopag were portal vein thrombosis (PVT). Symptoms of PVT included abdominal pain, nausea, vomiting, and diarrhea. Five of the six patients in the group that received eltrombopag experienced a thrombotic complication within 30 days of completing treatment with eltrombopag and at a platelet count above  $200 \times 10^9/L$ . The risk of portal venous thrombosis was increased in thrombocytopenic patients with chronic liver disease treated with 75 mg eltrombopag once daily for 2 weeks in preparation for invasive procedures.

### **2.3.4 Cataracts**

In the 3 controlled clinical trials in chronic ITP, cataracts developed or worsened in 15 (7%) patients who received 50 mg eltrombopag daily and 8 (7%) placebo-group patients. In the extension trial, cataracts developed or worsened in 4% of patients who underwent ocular examination prior to therapy with eltrombopag. In the 2 controlled clinical trials in patients with chronic hepatitis C and thrombocytopenia, cataracts developed or worsened in 8% patients treated with eltrombopag and 5% patients treated with placebo. Patients treated with eltrombopag who experience visual difficulties should have an appropriate ophthalmologic examination including evaluation for cataract formation.

### **2.4. Decitabine**

Decitabine is supplied as a lyophilized white to almost white, finely crystalline, odorless powder for injection in 20 mL glass vials, containing 50 mg of decitabine, monobasic potassium phosphate, and sodium hydroxide. When reconstituted with 10 mL of sterile water for injection each mL will contain 5 mg of decitabine, 6.8mg of  $KH_2PO_4$ , and approximately 1.1 mg NaOH. The pH of the resulting solution is 6.5-7.5. The reconstituted solution can be further diluted to a concentration of 1 mg/mL or 0.1 mg/mL in cold infusion fluids (0.9% Sodium Chloride Injection USP, 5% Dextrose in Water Injection, USP, or Lactated Ringer's Injection USP).

The intact vials should be stored under refrigeration (2-8°C; 36-46°F) in the original package. Shelf life surveillance of the intact vials is on-going. The intact vials are stable for at least 1 year at room temperature (22-25°C), 2 years at 2-8°C or 6 months at 40°C. Reconstitution and dilution of the powder for injection (with 10 mL of sterile water for injection) results in a rapidly decomposing solution. The concentration of decitabine in the reconstituted and diluted solution decreases about 10% after 4 hours at 25°C or

about 10% after 24 hours at 4°C. Since 10% is the maximum allowable decomposition, and the solution will also decompose during administration (infusion), the solution should be prepared just prior to administration. If this is not possible the solution should be prepared at least twice a day and be kept in a refrigerator (2-8°C) until administration. Furthermore, the solution should be prepared only with cold infusion fluids at a temperature of 2-8°C (36-45°F). The solution can be infused over a maximum period of 3 hours.

Drug handling precautions will be strictly followed. Skin contact with the solution should be avoided and protective gloves should be worn. Spilt drug can be inactivated by 2 M sodium hydroxide solution.

### **3. STUDY ELIGIBILITY**

#### **3.1 Inclusion Criteria**

1. Signed, informed consent must be obtained prior to any study specific procedures.
2. Subjects with a histologically confirmed diagnosis of MDS by FAB criteria, including both MDS and RAEB-T (AML with 20-30% blasts and multilineage dysplasia) and chronic myelomonocytic leukemia (CMML) with at least 10% bone marrow blasts by World Health Organization (WHO) classification are eligible.
3. Advanced MDS by virtue of intermediate-2 or high-risk MDS by IPSS score, or high or very-high risk by IPSS-R.
4. Platelet count  $\leq 100 \times 10^9/L$  at baseline
5. Eastern Cooperative Oncology Group (ECOG) performance status of 0 to 2
6. Adequate liver function, as evidenced by a serum bilirubin  $\leq 2x$  the ULN (except for patients with a confirmed diagnosis of Gilbert's Disease) and an ALT or AST  $\leq 3x$  the laboratory ULN.
7. Serum creatinine  $\leq 2.5x$  upper limit of normal
8. Subjects must be  $\geq 18$  years of age at the time of informed consent
9. Subject is practicing an acceptable method of contraception (documented in chart). Female subjects (or female partners of male subject) must either be of non-childbearing potential (hysterectomy, bilateral oophorectomy, bilateral tubal ligation or post-menopausal  $> 1$  year), or of childbearing potential and use one of the following highly effective methods of contraception (i.e. Pearl index  $< 1.0\%$ ) from 2 weeks prior to administration of study medication, throughout the study, and 28 days after completion or premature discontinuation from the study:

- Complete abstinence from intercourse;
- Intrauterine device (IUD);
- Two forms of barrier contraception (diaphragm plus spermicide, and for males condom plus spermicide);
- Male partner is sterile prior to entry into the study and is the only partner of the female;
- Systemic contraceptives (combined or progesterone only).

### 3.2 Exclusion Criteria

1. Subjects with any prior exposure to a thrombopoietin-receptor agonist
2. Prior hypomethylating agent treatment for MDS
3. Any prior or co-existing medical condition that in the investigator's judgment will substantially increase the risk associated with the subject's participation in the study
4. Psychiatric disorders or altered mental status precluding understanding of the informed consent process and/or completion of the necessary study procedures
5. Active uncontrolled serious infection or sepsis at study enrollment
6. Clinically significant gastrointestinal disorders that may interfere with absorption of drug.
7. History of arterial thrombosis (i.e. stroke) in the past year
8. History of venous thrombosis currently requiring anti-coagulation therapy
9. Unstable angina, congestive heart failure (New York Heart Association (NYHA) > Class II), uncontrolled hypertension (diastolic blood pressure > 100mmHg), or recent (within 1 year) myocardial infarction
10. Subjects with a QTc > 480 msec (QTc > 510 msec for subjects with Bundle Branch Block) at baseline
11. Pregnant or breast-feeding
12. Subjects with known history of human immunodeficiency virus (HIV) or active infection with hepatitis C virus (HCV) or hepatitis B virus (HBV), because eltrombopag is hepatically cleared, and underlying hepatic impairment may lead to an increased risk of hepatotoxicity. Eltrombopag has not been evaluated with combination antiretroviral regimens.
13. Subjects with liver cirrhosis (as determined by the investigator)

14. Subjects with hypersensitivity to study drugs or their excipients.

## **4. TREATMENT PLAN**

### **4.1 Study Design**

This is a single arm phase II study of eltrombopag in combination with decitabine in subjects with thrombocytopenia and higher risk (advanced) myelodysplastic syndromes (MDS). The purpose of this study is to explore the supportive care and disease-modifying effects of eltrombopag in combination with decitabine standard of care for patients with advanced MDS. The primary objective will be the overall response rate (ORR) based on the IWG-2006 criteria, which includes complete remission (CR), partial remission (PR), and hematologic improvement (HI).

The primary endpoint will be evaluated for each 28-day cycle of decitabine treatment during the first four cycles, and these 4 cycles will be used for the primary analysis. Four cycles of the primary endpoint was chosen since the median duration to decitabine response is 3.3 cycles, and the occurrence or worsening of thrombocytopenia in patients treated with hypomethylating agents is most commonly observed in the initial cycles of treatment. Adverse events, bleeding events, and concomitant medications will be assessed continually throughout the study; specific information will be requested at every study visit.

A total of 40 patients will be accrued from M. D. Anderson Cancer Center (MDACC).

#### **4.1.1. Study Replacement:**

All patients who receive at least one dose of the study drug will be included in the efficacy and safety analysis. For efficacy analysis, patients who drop out of the study early (i.e. before the end of cycle 1) due to treatment-related toxicities will be counted as treatment failures (i.e. non-responders). Patients will be replaced if they drop out of the study before receiving any dose of the study drug.

### **4.2. Study Duration**

4.2.1. All subjects must complete a screening visit, day 1 visits for each new cycle, an end of treatment visit and whenever possible, an end of study safety visit 28 days after the last dose of eltrombopag.

4.2.2. Treatment will continue until discontinuation due to relapse, unacceptable toxicity, or disease progression as defined by the IWG 2006 criteria for MDS. This includes:

- clinically significant progressive disease at any time, or

- a lack of clinical benefit after 4 cycles of treatment at the highest dose of study medication, or
- Possibility of undergoing allogeneic stem cell transplantation
- discontinuation of study drug for more than 6 weeks, or
- intercurrent illness that prevents further administration of treatment, or
- unacceptable adverse event(s), or
- patient decision for study withdrawal, or
- general or specific changes in the patient's condition that render the patient unacceptable for further treatment in the judgement of the investigator

4.2.3. Study cycles will be administered every 28 days  $\pm$  5 days or upon resolution of any clinically significant study drug related AE to grade 0-1, whichever occurs first. If a subsequent cycle is delayed due to adverse events related to decitabine, or if it is considered in the best interest of the patient to delay administration of decitabine (e.g. because of concern for an infection), administration of the eltrombopag may continue as planned.

4.2.4. Administration of subsequent cycles should be administered when neutrophils recover to  $\geq 1 \times 10^9/L$  and platelets to  $\geq 30 \times 10^9/L$  or to baseline levels prior to the start of the last cycle of therapy. Patients with residual disease may start the next cycle with neutrophil and/or platelet counts lower than these if judged to be in the best interest of the patient to start the next cycle. The decision to treat should be documented in the patient's medical record.

4.2.5. Patients may remain on study for up to 12 cycles if the patient demonstrates clinical benefit and no excessive toxicity (i.e. no clinically significant study-drug related grade  $\geq 3$  toxicity). Patients who are experiencing clinical benefit and have not experienced excessive toxicity may be eligible to continue therapy after discussion with the PI and the discussion documented in the patient's medical record.

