#### 4.8 Dosing Delays and Dose Modifications

##### 4.8.1. Dose Adjustments for Toxicity:

The doses of eltrombopag and decitabine will be adjusted according to the guidelines shown in the following tables for study drug-related clinically significant toxicity. If toxicity is not covered in the table, doses may be reduced or held at the discretion of the investigator for the patient's safety. See section 4.8.4 for liver chemistry stopping and follow-up criteria.

Patients will be withdrawn from the study if they fail to recover to CTCAE grade 0 to 1 (or within 1 grade of starting values for pre-existing laboratory abnormalities) from a clinically significant non-hematologic treatment-related toxicity within 6 weeks (leading to treatment delay of > 4 weeks) unless the investigator feels that the patient should remain in the study because of evidence that the patient is/may continue deriving benefit from continuing study treatment. Such instances will be discussed with the principal investigator on a case by case basis and the discussion documented in the medical record.

Patients with study-drug related toxicities that are manageable with supportive therapy may not require dose reductions. For patients with other drug-related toxicities, the following dose adjustment rules apply:

NCI CTCAE Grade	Action
Grade 0-2 non-hematological toxicity	No dose reduction.  For grade 2 toxicities that are persistent and/or intolerable (e.g. stomatitis) patients may have a treatment interruption or dose

	reductions to the next lower dose level.
Grade 3-4 clinically significant non-hematological toxicity†	Hold until recover to NCI CTC AE grade 0-1  If recovery occurs within 2 weeks after treatment has been held, dose should be reduced to -1 dose level, if applicable.

† see 4.8.4 for additional liver chemistry stopping and follow-up criteria

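### The cycle-start rule in 4.2.3 takes the earlier of two dates, which contradicts the 4.8.1 hold for grade 3-4 non-hematological toxicity; for held cases it should take the later

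*Combined protocol and SAP*

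**What the plan says.** Section 4.2.3 (Study Duration) gives two triggers for the next cycle: the calendar, at 28 ± 5 days, or "upon resolution of any clinically significant study drug related AE to grade 0-1, whichever occurs first". The next sentence of 4.2.3 begins "If a subsequent cycle is delayed due to adverse events related to decitabine" and goes on to allow eltrombopag to continue meanwhile.

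Section 4.8.1 (Dose Adjustments for Toxicity) applies to both eltrombopag and decitabine. Toxicities that supportive therapy can manage may need no dose reduction. The table is then introduced with "For patients with other drug-related toxicities, the following dose adjustment rules apply". Its row for "Grade 3-4 clinically significant non-hematological toxicity" reads "Hold until recover to NCI CTC AE grade 0-1". The grade 0-2 row requires no reduction; for persistent or intolerable grade 2 toxicity, "patients may have a treatment interruption" or a reduction.

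Sections 4.2.4 and 4.8.2.3 separately make the next cycle wait for neutrophil and platelet recovery, with an exception for residual disease.

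**The concern.** An AE clause in a cycle-start rule is normally there to postpone dosing until the patient has recovered. Joined to the calendar by 'first', it cannot do that: when recovery is late, the calendar date is the earlier one and governs. The sentence then makes a cycle due while 4.8.1 says treatment is on hold.

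What is at stake is patient safety and the clarity of a dosing instruction. Section 4.3 allows decitabine to be given by local doctors, so the rule should read correctly without being reconciled against a later section. The efficacy estimate and the design's statistical properties are not in question.

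**Working it through.** The plan gives no figure to reproduce. The check is whether one start date can satisfy both rules.

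**Inputs.** Days are counted from the start of the previous cycle.
- Calendar window (4.2.3): 28 − 5 = day 23 to 28 + 5 = day 33. Let d be the scheduled day, 23 ≤ d ≤ 33.
- Let r be the day the toxicity reaches grade 0-1. The documents give no values for r.
- Connector in 4.2.3: the earlier date governs.
- Hold in 4.8.1: no dosing before r, for a grade 3-4 clinically significant non-hematological toxicity.

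**The rules as formulas.**
- 4.2.3 as written: start = min(d, r).
- 4.8.1: start ≥ r.
- With 'last' for held cases: start = max(d, r).

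**Comparison.**
1. If r ≤ 33, a start on day r is open under both rules, so there is no contradiction with the hold.
2. If r > 33, then d ≤ 33 < r, so min(d, r) = d. The start falls on days 23-33 whatever r is, and the AE clause has no effect. The hold requires day r or later. No date meets both.
3. With max(d, r) and r > 33, the start is day r, as the hold requires.

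**Size of the gap.** For r > 33, literal 4.2.3 doses r − 33 to r − 23 days before recovery. Two assumed recovery days, for illustration only:

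| Assumed r | Start under 4.2.3 as written | Days before recovery | Start under 'last' |
|---|---|---|---|
| 42 | day 23-33 | 42 − 33 = 9 to 42 − 23 = 19 | day 42 |
| 45 | day 23-33 | 45 − 33 = 12 to 45 − 23 = 22 | day 45 |

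Nothing in the documents says how often a held toxicity would last past day 33.

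**Check against the rest of 4.2.3.** The following sentence deals with cycles delayed by decitabine-related AEs. Under min(d, r), an AE cannot move a start beyond the window, so that sentence would have little to act on. It shows that AE-driven delay was intended and that 'first' is the slip.

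**Why 'last' must be limited to held cases.** The AE clause in 4.2.3 covers any clinically significant drug-related AE. Swapping the word throughout would delay cycles for unresolved grade 2 events, where 4.8.1 makes interruption optional, and could catch drug-related cytopenias, which 4.2.4 and 4.8.2.3 already handle with their own exception.

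**The case against.** The strongest reply is that nobody would be misled. Section 4.8.1 is specific, applies to both drugs and says to hold. Count recovery in 4.2.4 is naturally read as qualifying 4.2.3, so 4.8.1 can be read the same way. Section 4.8.2.3 gives decitabine start conditions without repeating 'first', and 4.8.2.5 accepts other delays after discussion. The procedures table in 5.2 schedules examination, chemistries and AE assessment on Day 1 of each cycle, and 4.2.2 ends treatment for unacceptable AEs.

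Most of this stands, and it is why the practical risk is low. It does not remove the contradiction. Count recovery adds a separate condition; 4.2.3 and 4.8.1 address the same event, recovery to grade 0-1, and point in opposite directions. No text gives 4.8.1 precedence. Section 4.5.2 requires approval for changes to decitabine dose or schedule, and dosing on day 28 under 4.2.3 is not a change.

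A reader might infer more than the text supports:
- **That 4.2.3 caps delay at a few days while 4.8.1 allows more than four weeks.** The words "within 6 weeks (leading to treatment delay of > 4 weeks" belong to a withdrawal rule, with a case-by-case exception. They describe failure to recover and do not set an ordinary permitted delay, so the two figures are not comparable.
- **That early recovery would trigger an early cycle.** Section 4.8.2.1 fixes a 28-day cycle and count recovery would normally still be needed, so this is largely theoretical.
- **That local doctors would dose through toxicity.** Section 4.3 refers to a letter to local physicians in Appendix E that is not in the text reviewed. What they were told is unknown.

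**Conclusion.** The point holds as a wording error in an operative dosing rule. For a grade 3-4 clinically significant non-hematological toxicity held under 4.8.1 and unresolved at day 33, 4.2.3 as written and 4.8.1 cannot both be followed; the next sentence of 4.2.3 shows which was meant. The conclusion rests on a literal reading of 'first' and on the absence of any stated order of precedence.

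The practical risk is small. A reader might infer that the protocol deliberately directs dosing through toxicity, or that the response rate, stopping boundaries or operating characteristics are affected. The documents support neither: 4.8.1 states the hold plainly, and the boundaries and operating characteristics in Section 8 are set by patient counts, prior distributions and assumed rates, not by cycle start dates. No statistical figure changes.

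**What to change.** Replace the cycle-start sentence in 4.2.3 with wording such as:

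> Each cycle starts 28 ± 5 days after the start of the previous one, subject to count recovery under 4.2.4 and any interruption under 4.8.1; if decitabine is being held under 4.8.1 for a grade 3-4 clinically significant non-hematological toxicity, the next cycle starts at 28 ± 5 days or on recovery to grade 0-1 as 4.8.1 requires, whichever is later.

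Three features matter. The count-recovery and optional grade 2 provisions are inside the sentence. The trigger is that decitabine is being held, so a toxicity for which only eltrombopag is held does not by itself delay decitabine; the 4.8.1 table does not say which drug is held, and the new sentence leaves that clinical decision where it is. The recovery standard is the one in the hold row. The allowance "or within 1 grade of starting values for pre-existing laboratory abnormalities" stands only in the withdrawal sentence of 4.8.1 and should not be carried into the hold unless the principal investigator separately decides to.

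The cost is one sentence of amendment text, with no added procedures, patients or analyses.
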